2.4.5. Pharmacokinetic Analysis Set

The PK Analysis Set includes all subjects, regardless of their compliance with the protocol, who received at least 1 dose of intranasal esketamine and at least 1 evaluable concentration data.

2.4.6. Pharmacokinetic/pharmacodynamic (PK/PD) Analysis Set

Blood pressure (DBP and SBP) and QTcF will be selected for safety parameter. The PK/PD analysis set includes all subjects who received at least 1 dose of intranasal esketamine, and have at least 1 time point with nominal time-matched plasma concentration and safety parameter.

2.5. Definition of Subgroups

Analyses will be provided for the primary endpoint, changes from baseline in MADRS total score, using the following subgroups.

- Sex
- Age Group (<45 years, ≥45 years)
- Number of Previous Treatments in Current Episode
- Functional Impairment based on Baseline SDS Total Score (not impaired [0-3], mild [4-11], moderate [12-19], marked [20-26] or extreme [27-30])
- Baseline MADRS total score (≤/≥ Median)
- Class of oral antidepressant (SNRI, SSRI or mirtazapine)
- BMI (≤/≥ Median)
- Number of major depressive episodes including current episode (1, 2-3, 3<)
- Duration of the current episode (≤ 26, >26-52, >52-104, >104 weeks)
- Concomitant use of benzodiazepine excluding sleep aids (Y/N)
- Concomitant use of benzodiazepine including sleep aids (Y/N)
- Had been considered to be eligible for electroconvulsive therapy (Y/N)

2.6. Imputation Rules for Missing Adverse Event (AE) Dates

Treatment-emergent adverse events (TEAEs) are those events with an onset date/time on or after the start of study medication during induction phase (DB/OL), and occurred on or before the end of the corresponding induction phases (DB/OL). Adverse events (AEs) for the follow-up (DB/OL) phase are those events with an onset date on or after the start of the follow-up (DB/OL) phase, and occurred on or before the end of the follow-up (DB/OL) phase. Adverse events (AEs) for the posttreatment phase are those events with an onset date on or after the start of the posttreatment phase, and occurred on or before the end of the posttreatment phase. A conservative approach will be used to handle the missing dates for adverse events.

Onset Date

If the onset date of an AE is missing day only, it will be set to:

1. First day of the month that the AE occurred, if month/year of the onset of AE is different than the month/year of DB start date
2. The day of DB start date, if the month/year of the onset of AE is the same as month/year of the DB start date and month/year of the AE resolution date is different
3. The day of DB start date or day of AE resolution date, whichever is earliest, if month/year of the onset of AE and month/year of the DB start date and month/year of the AE resolution date are the same.

If the onset date of an AE is missing both day and month, it will be set to the earliest of:

1. January 1 of the year of onset, as long as this date is after the DB start date.
2. One day after the DB start date, if this date is the same year that the AE occurred.
3. The day of AE resolution date, if this date is the same year that the AE occurred.

A completely missing onset date of an adverse event will be set to the day of DB start date or day of AE resolution date, whichever is earliest.

Similar rules will be applied for OL missing onset date.

Resolution Date

The missing day of resolution of an AE will be set to the last day of the month of resolution.

If the resolution date of an AE is missing both day and month, it will be set to the earlier of the date of withdrawal, study completion, or December 31 of the year.

A completely missing resolution date of an AE that is not recorded as ongoing will be set to the date of study completion/discontinuation.

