11.8. Safety Analyses

Safety analysis set will consist of all randomized subjects who receive at least 1 dose of intranasal study drug in the double-blind induction phase. Safety data for the double-blind period will be analyzed for this population. For the analysis of safety data in the OL induction phase, all subjects who received at least 1 dose of intranasal study drug in this period will be analyzed.

Adverse Events

For each AE, the number of subjects who experience at least 1 occurrence of the given event will be summarized by treatment group.

The verbatim terms used in the eCRF by investigators to identify AEs will be coded using the Medical Dictionary for Regulatory Activities (MedDRA). The TEAEs are AEs with onset during the treatment phase or that are a consequence of a preexisting condition that has worsened since baseline. All reported AEs will be included in the analysis. For each AE, the percentage of subjects who experience at least 1 occurrence of the given event will be summarized by treatment group. In addition, comparisons between treatment groups will be provided if appropriate.

The TEAEs of special interest will be examined separately (please refer to Section 3.2.6). The AEs of special interest will be further listed in the SAP.

Summaries, listings, datasets, or subject narratives may be provided, as appropriate, for those subjects who die, who discontinue treatment due to an AE, or who experience a severe or an SAE.

Clinical Laboratory Tests

Laboratory data will be summarized by type of laboratory test. Markedly abnormal results (specified in the SAP) will be used in the summary of laboratory data. Descriptive statistics will be calculated for each laboratory analyte at each respective scheduled time point in each phase of the study. Changes from baseline results will be presented. Frequency tabulations of the abnormalities will be made. A listing of subjects with any markedly abnormal laboratory results will also be provided.

Electrocardiogram (ECG)

The effects on cardiovascular variables will be evaluated by means of descriptive statistics and frequency tabulations. These tables will include observed values and changes from baseline values.

Electrocardiogram data will be summarized by ECG parameter. Descriptive statistics will be calculated at baseline and for observed values and changes from baseline at each scheduled time point. Frequency tabulations of the abnormalities will be made.

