5.1. Adverse Events

The Medical Dictionary for Regulatory Activities (MedDRA) (version 20.0 or above) will be used to classify adverse events (AEs) by system organ class and preferred term. Treatment-emergent adverse events (TEAEs) that occurred in each analysis phase (DB induction, DB follow-up, PT, OL induction, OL follow-up) will be summarized by system organ class and preferred term.

The number (%) of subjects with TEAEs, serious TEAEs (SAEs), and TEAEs that led to study drug discontinuation, dose reduction will be summarized by system organ class and preferred term. TEAEs will be summarized by onset time (4 week intervals). Data listings will be generated for deaths, other SAEs, and discontinuations due to AEs.

A TEAE is an event that is new in onset or increased in severity following treatment initiation. An event that starts prior to, and ends after the initiation of study medication will be considered treatment-emergent only if the severity increases after the start of medication.

Treatment-emergent adverse events (TEAEs) are defined as follows for each analysis phase:

- TEAEs in DB induction phase:
 - a. If AE onset time is not missing: DB start date/time \leq AE onset date and time \leq DB end date
 - b. If AE onset time is missing: DB start date \leq AE onset date \leq DB end date
- TEAEs in OL induction phase:
 - a. If AE onset time is not missing: OL start date/time \leq AE onset date and time \leq OL end date
 - b. If AE onset time is missing: OL start date \leq AE onset date \leq OL end date
- AEs in DB follow-up phase: DB FU start date \leq AE onset date \leq DB FU end date
- AEs in OL follow-up phase: OL FU start date \leq AE onset date \leq OL FU end date

- For the AEs that have both day and month missing, treatment-emergent flag is assigned based on the rules presented in Section 2.6.

In addition, TEAEs will be summarized by severity and relationship to study medication using the preferred term. For the summaries of TEAEs by severity/relationship to study medication, the observation with the most severe occurrence/closest relationship to study medication will be chosen if there is more than one incident of an AE reported during the analysis phase by the subject.

Adverse Events of Special Interest

Clinically relevant TEAEs of special interest will be examined separately grouped in the following categories:

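### The SAP's date rules for treatment-emergent AEs omit the worsening clause that its own Section 5.1 narrative and Protocol 11.8 contain, and no precedence is stated

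*SAP*

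**What the plan says.** Four statements bear on what counts as a TEAE.

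- **SAP 2.6**, which otherwise deals with missing AE dates, opens with a definition: "Treatment-emergent adverse events (TEAEs) are those events with an onset date/time on or after the start of study medication". It adds that the event must occur by the end of the corresponding induction phase. It does not mention worsening.
- **SAP 5.1, phase rules.** These are introduced with "Treatment-emergent adverse events (TEAEs) are defined as follows for each analysis phase". For the DB phase the first condition begins "If AE onset time is not missing: DB start date/time" and requires the AE onset to lie between that point and the DB end date. A date-only version applies when the onset time is missing. The OL rule has the same form. Severity plays no part in either.
- **SAP 5.1, narrative**, just above the phase rules: "A TEAE is an event that is new in onset or increased in severity following treatment initiation". An event that was under way when study medication began "will be considered treatment-emergent only if the severity increases after the start of medication".
- **Protocol 11.8** counts AEs with onset in the treatment phase and also those "that are a consequence of a preexisting condition that has worsened since baseline".

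SAP 2.1.2 sets the DB start at the first intranasal dose and the OL start at the first dose of the second course. Protocol 12.1.1 starts AE collection at signature of the consent form.

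**The concern.** The first two statements classify by onset date alone. The last two classify by onset or worsening. A fully dated event that began before the phase and became more severe on study drug is a TEAE under one pair and not under the other.

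This design makes such events plausible. Every subject starts a new oral antidepressant in the six-week lead-in, with titration toward the approved maximum dose, and AEs in that period are recorded with pre-dose onset dates. The common esketamine events listed in Protocol 1.1.2 include nausea, headache, somnolence and dizziness, and some of these could already be present from the antidepressant. In the OL phase the same question arises for AEs that begin in the posttreatment phase.

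The summaries exposed are the induction-phase TEAE tables by preferred term, by severity and by relationship, and the special-interest groupings, which include dizziness, somnolence and anxiety terms. TEAEs are named under the secondary safety objectives.

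**Working it through.** The plan gives no figure to reproduce here, so the check applies each written rule to test cases. Full onset dates are assumed, and each AE keeps its original onset date.

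| Case | SAP 2.6 | SAP 5.1 phase rule | SAP 5.1 narrative | Protocol 11.8 |
|---|---|---|---|---|
| A. Onset Day -10, mild, ongoing at first dose, severe from Day 4 | No | No | Yes | Yes |
| B. Onset Day 4 | Yes | Yes | Yes | Yes |
| C. Onset Day -10, ongoing, severity unchanged | No | No | No | No |
| D. Onset in the posttreatment phase, ongoing at first OL dose, worse during OL (classified for the OL phase, against OL baseline) | No | No | Yes | Yes |

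1. The rules agree on B and C and split on A and D. Worsening of an existing event is the only point of disagreement.
2. Case A cannot meet the date rules however much it worsens, because DB start is the first dose and Day -10 precedes it. The five analysis phases in SAP 2.1 all begin at or after the first dose, so no phase-specific AE table would hold the event.
3. Case D is not lost altogether. By its onset date it falls in the posttreatment phase, but it is absent from the OL table, where the worsening took place.
4. With the worsening clause added to the date rules, A and D become TEAEs under all four statements, and B and C do not change.

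**A side effect of the date imputation.** Under SAP 2.6, an AE whose onset day is missing, whose onset month is that of DB start and which resolves in a later month is given the DB start date. A partly dated lead-in AE of this kind can be flagged as a TEAE with no worsening, while a fully dated one that does worsen (Case A) is not flagged.

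**Scale.** The documents give no rate for AEs ongoing at Day 1 or for worsening. Protocol 11.2 plans 37 subjects per esketamine arm and 72 on placebo. One subject is therefore 1/37 = 2.7 percentage points of an esketamine arm and 1/72 = 1.4 points of placebo. As a pure assumption, suppose 20–40% of subjects have an AE ongoing at Day 1 and 5–15% of those worsen. The share affected is then 0.20 × 0.05 = 1% to 0.40 × 0.15 = 6%, or 37 × 0.01 = 0.4 to 37 × 0.06 = 2.2 subjects per esketamine arm. These inputs come from no source in the documents and show the order of magnitude only.

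**The case against.** The strongest reply is that SAP 5.1 already covers the case. Its narrative sits immediately above the phase rules, names the worsening case and agrees with the protocol. The natural reading is that the narrative decides what is treatment-emergent and the date rules only assign events to phases. Section 2.6 is about imputing dates. This stands against one tempting inference, that the plan uniformly excludes worsened events. It does not: half of its statements retain them. The reply does not remove the conflict. The phase rules are introduced as the definition, not as an allocation step. Even as an allocation step, they give Case A no phase to belong to.

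A second reply concerns recording. Protocol 12.1.1 includes aggravation from the baseline condition within the AE definition. Protocol 8 sends a new or worsening condition that is treated with medication to the AE section of the eCRF, and Protocol 9.6 requires clinically relevant changes to be recorded there. If worsening is entered as its own AE with its own onset, the date rules capture it. That is plausible, but neither document prescribes it. The CRF completion guideline, named in Protocol 15, is not among the documents.

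Third, the mechanism may be modest. Protocol 1.1.2.3 describes esketamine AEs as transient, typically resolving within two hours, so many would be recorded as fresh episodes after a dose. Blood pressure, pulse, CADSS, BPRS+ and MOAA/S are summarised against predose values without reference to the TEAE flag. The listings of deaths, other SAEs and discontinuations due to AEs are not worded as TEAE-only. A subject with any other TEAE is already counted in the overall row. All of this limits the likely effect and is accepted.

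A reader might also infer that the omission favours esketamine. The documents do not support that. The rule is identical in every arm, and a direction follows only from assuming that worsening is more frequent on esketamine than on placebo.

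**Conclusion.** The point holds as an unresolved contradiction in the current text. SAP 2.6 and the DB and OL rules of SAP 5.1 define a TEAE by onset date alone. The SAP 5.1 narrative and Protocol 11.8 also count worsening, and nothing says which governs. A programmer who follows the date rules literally would leave Case A and Case D out of the induction-phase TEAE tables, which is wrong by the plan's own definition.

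The conclusion assumes that the AE record keeps its original onset date when severity changes. If sites open a new record with the date of worsening as its onset, the effect is nil. The number of events affected and any difference between arms cannot be determined from the documents. The case for change rests on the inconsistency and on how little it costs to remove.

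**What to change.** In SAP 2.6 and in the DB and OL rules of SAP 5.1, add to the date condition: *or an AE with onset before the phase start, ongoing at phase start, whose severity increases on or after the phase start date/time and by the phase end date*.

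Apply this through one recording convention, stated in the SAP and the CRF completion guideline:

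- either worsening is entered as a new AE record whose onset is the date of worsening; or
- the original record carries the date of the severity increase.

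Using both would risk counting one worsening twice, once through the amended rule and once as the new record.

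The cost is one clause in two SAP sections and a line in the guideline. Under the second option, confirm that the eCRF captures the date of a severity change; the documents do not show that it does, and adding it would cost more than a wording edit. TEAE counts may rise slightly. Events with onset on treatment, and pre-existing events that do not worsen, keep their classification.

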2.7. Imputation Rules for Missing AE Time of Onset/Resolution

If the time of onset is missing, it will be imputed as follows:

1. 00:00 if the date of onset is after DB start date
2. The time of intranasal medication start in the double-blind induction phase

If the time of resolution is missing, it will be set to 23:59

If a missing time is associated with a partial or missing date, the date will be imputed first prior to imputing the time.

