2.1.2. Analysis Phase Start and End Dates

Double-blind Induction Phase

The start date of the double-blind induction phase (referred to as ‘DB start date’) is the date of the first dose of intranasal study medication. The double-blind induction phase end date (referred to as ‘DB end date’) is the maximum of the date of the last visit in the double-blind induction phase and the date of completion/withdrawal from the double-blind induction phase.

The start date/time of the double-blind induction phase (referred to as, ‘DB start date/time’) is the DB start date and the time of the first dose of intranasal study medication.

Double-blind Follow-up Phase

The start date of the double-blind follow-up phase (referred to as ‘DB FU start date’) is the day after the DB end date. The double-blind follow-up phase end date (referred to as ‘DB FU end date’) is the maximum of the last DB follow-up visit date or the end of trial date.

Posttreatment Phase

The start date of the posttreatment phase (referred to as ‘PT start date’) is the day after the DB end date. The posttreatment phase end date (referred to as ‘PT end date’) is defined as: for subjects who entered OL phase, the day of OL start date (defined below); for subjects who did not enter OL, including responders who withdraw within 4 weeks after the last dose of DB intranasal drug, the maximum of the last posttreatment visit date or the end of trial date.

For subjects who entered OL phase, PT end date/time is one minute before OL start date/time (defined below).

Open-Label Induction Phase

The start date of the open-label induction phase (referred to as ‘OL start date’) is the date of the first dose of intranasal study medication in a second induction treatment course. The open-label induction phase end date (referred to as ‘OL end date’) is the maximum of the date of the last visit in the open-label induction phase and the date of completion/withdrawal from the open-label induction phase.

The start date/time of the open-label induction phase (referred to as, ‘OL start date/time’) is the OL start date and the time of the first dose of intranasal study medication in the second induction treatment course.

Open-Label Follow-up Phase

The start date of the open-label follow-up phase (referred to as ‘OL FU start date’) is the day after the OL end date. The open-label follow-up phase end date (referred to as ‘OL FU end date’) is the maximum of the last OL follow-up visit date or the end of trial date.

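### A missing AE onset time on the first open-label dosing day is imputed to 00:00, before the dose, so the event is counted in the posttreatment phase

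*SAP*

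**What the plan says.** SAP 2.7 has two branches for a missing onset time. The first gives "00:00 if the date of onset is after DB start date". The second, left for the DB start date, gives "The time of intranasal medication start in the double-blind induction phase". When the date is missing too, the date is imputed before the time.

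SAP 2.6 carries its rules over to open label with one sentence, "Similar rules will be applied for OL missing onset date", which concerns dates. SAP 2.7 has no such sentence for times. SAP 2.6 also says: "Adverse events (AEs) for the posttreatment phase are those events with an onset date on or after the start of the posttreatment phase". A second limb of that sentence requires the event to have occurred by the end of the posttreatment phase.

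SAP 2.1.2 sets the PT end date as follows: "for subjects who entered OL phase, the day of OL start date". For the same subjects it also defines a PT end date/time, one minute before the OL start date/time, which is the time of the first OL dose.

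SAP 5.1 gives two rules for OL treatment-emergent events. Rule (a) has the lower bound "If AE onset time is not missing: OL start date/time". Rule (b), for a missing time, compares dates only. Section 5.1 names PT among the phases for which AEs are reported, but its list of phase definitions has no PT entry.

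**The concern.** PT to OL is the one phase change that happens within a single calendar day. DB follow-up, PT and OL follow-up each start on the day after the preceding phase ends. On the shared day, phase assignment depends on clock time, and the clock-time rule in 2.7 was written with only the DB phase in mind.

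That day is also the first re-exposure. Protocol 1.1.2.3 describes esketamine AEs as transient and typically gone within 2 hours of the start of dosing. Protocol 3.2.4 notes that dissociation lessens on repeated dosing. Responders from the placebo arm can also relapse and enter OL, so for them it is a first exposure.

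An acute event assigned to PT is reported as if it arose off intranasal drug, under the randomized arm. At stake are the withdrawal and rebound description (a secondary safety objective) and the comparison of the DB and OL courses (an exploratory one). No efficacy result is involved.

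**Working it through.** No planned figure is at issue, so the check applies the rules literally to test events. Assume for illustration that the first OL dose is at 10:00. The OL start date/time is then 10:00 and the PT end date/time is 09:59. Any dose time later than 00:01 gives the same result.

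1. **Which branch of 2.7 applies.** Protocol 6.4.1 starts OL at least 14 calendar days after the last DB dose. The OL start date is therefore always after the DB start date, and a missing time always becomes 00:00.
2. **Posttreatment, time missing.** By date, the onset date equals the PT end date, so the event is in PT. By date/time, 00:00 is before 09:59, so it is again in PT.
3. **Open label, time missing.** Under 5.1(a) with the imputed time, 10:00 ≤ 00:00 is false, so it is not an OL event. Under 5.1(b), the onset date equals the OL start date, so it is.
4. **Comparison event, recorded at 10:40.** It is an OL event under 5.1(a). It is in PT by date (same calendar day), but not by date/time, because 10:40 is after 09:59.

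| AE on the OL start date | PT, cut by date | PT, cut by date/time | OL, 5.1(a) | OL, 5.1(b) |
|---|---|---|---|---|
| Time missing, imputed 00:00 | yes | yes | no | yes |
| Time recorded, 10:40 | yes | no | yes | not applicable |

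5. **The DB counterpart.** A missing time on DB Day 1 is set to the dose time, which equals the DB start date/time, so the event is treatment-emergent. The OL phase lacks this protection.
6. **Partial dates.** If the OL date rule mirrors the DB one, an AE with the day missing in the OL start month can be set to the OL start date. Section 2.7 then adds 00:00, which moves it ahead of the dose.

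**Scale.** The documents give no rate of entry into OL, no AE rate on that day, and no frequency of missing times. For orientation only, assume that 30–60% of PT subjects enter OL, that 40–70% of those have an AE on the first OL day, and that 2–10% of those AEs lack a time (one per subject):

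- low: 0.30 × 0.40 × 0.02 = 0.0024, about 0.2 per 100 PT subjects;
- high: 0.60 × 0.70 × 0.10 = 0.042, about 4.2 per 100 PT subjects.

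All three ranges are assumptions. The result is a ceiling on the rise in PT incidence, since an affected subject may have another PT event anyway.

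**The case against.** A reader might infer that acute AEs on the first OL day in general, including those with a recorded postdose time, enter the PT table. The text does not support that. In 2.6 the word date belongs to the start limb, and the end limb refers to the end of the phase. SAP 2.1.2 fixes that end to the minute for subjects entering OL, a precision given to no other phase end. Its evident purpose is to separate PT from OL on the shared day. The onset-date wording has an innocent explanation: PT has a start date but no start date/time. What remains is that 5.1 has no PT entry and 2.6 does not name the PT end date/time, so a date-only program is possible but probably not intended.

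A reader might also infer that missing-time events disappear from the OL table. Rule 5.1(b) is written for exactly these events and counts them in OL. If 2.7 always ran first, 5.1(b) would have nothing to act on, so the reading that gives every rule an effect keeps them in OL. That answers the loss. It does not answer the PT count, which follows under either cut.

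It is also fair to say that such records should be uncommon. OL dosing is supervised, with sedation scored every 15 minutes to 1.5 hours and dissociation at 40 minutes and 1.5 hours (Time and Events Schedule 3). Withdrawal has its own instrument, the PWC-20, which AE time imputation does not touch. These points limit the size of the error but do not remove it.

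**Conclusion.** The concern holds in a narrow form. A stated rule, applied as written, puts a missing-time AE on the OL start date into the wrong phase, and neither way of closing PT corrects it. Whether the event is also in OL depends on an order between 2.7 and 5.1 that the SAP does not give, so two programmers could produce different tables.

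The consequence is limited to descriptive PT and OL AE summaries in subjects who relapse and enter OL. Its size cannot be derived from the documents and is probably small if the PT end date/time is used.

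A much larger figure is tempting. With the same assumed ranges and a date-only PT cut, 0.30 × 0.40 = 12% to 0.60 × 0.70 = 42% of PT subjects would carry an AE from the first OL day. That range should not be used as an estimate. It multiplies two assumptions, needs a reading that 2.1.2 speaks against, and would raise PT incidence by that much only if no affected subject had any other PT event.

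**What to change.** Make two additions to the SAP:

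- **Section 2.7:** if the onset date equals the OL start date and the onset time is missing, set the time to that of the first OL dose.
- **Section 5.1:** add a PT entry. For subjects who enter OL, an AE belongs to PT if its onset is on or after the PT start date and its onset date/time is no later than the PT end date/time. For all other subjects, use the PT start and end dates.

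In the example, the missing time becomes 10:00. That meets 5.1(a) and 5.1(b) and lies after 09:59, so the event is in OL only and the order of 2.7 and 5.1 no longer matters for it. The 10:40 event is also in OL only. An event that truly began before the dose but has no recorded time would go to OL, the same convention that 2.7 already uses on DB Day 1.

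The cost is two sentences and a small change to the derivation program. No new data are needed.
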